## Form B: Medical IRB Research Description

### 8. Resources:

The research procedures will be conducted at UK Chandler Medical Center and University of Kentucky Plastic Surgery Clinic E-101 (Wing C, First Floor) [name]. The participants will be followed by [name] and her research team which includes physicians and certified nurse practitioners and clinical research coordinators during the study. Emergency medical equipment, medications, and supplies will be at the physician's disposal should the participant have an acute untoward reaction.

### 9. Potential Risks:

- **ChloroPrep:** Blistering, burning, itching, peeling, skin rash, redness, swelling, or other signs of irritation on the skin, swelling of the face, hands, or feet, trouble breathing. A severe allergic may occur and could lead to death.

- **Allergan Natrelle Style 133V Tissue Expanders**

General Known Risks: Any invasive surgical procedures has risks such as infection, hematoma, dysesthesia, postoperative pain and delayed healing.

Specific Known Risks:

**Magnetic field.** The MAGNA-SITE® integral injection site contains a rare-earth, permanent magnet. If you already have an implanted device that would be affected by a magnetic field (e.g., pacemaker, drug infusion device, artificial sensing device) you must not have a MAGNA-SITE® tissue expander implanted. In addition, patients with MAGNA-SITE® expanders in place should not undergo diagnostic testing with Magnetic Resonance Imaging (MRI).

**Deflation.** The expander and injection site may leak as a result of damage from surgical instruments or trauma. Deflation release the saline filling and will require surgery to replace the expander to continue with the expansion process.

**Tissue damage.** Tissue damage may occur if the overlying skin is too weak to tolerate the pressure of expansion. Tissue damage is most likely to occur with expansion against an unstable wound or tissue area, or expansion that occurs too rapidly, causing ischemia.

**Extrusion.** Extrusion of the expander may occur as a result of tissue damage. Extrusion may require removal of the expander.

**Capsular contracture.** The scar tissue that normally forms around any implanted device, including tissue expanders, may tighten and become firm around the expander. Capsular contracture may make expansion difficult and painful, and necessitate surgical intervention.

**Premature explantation.** Adverse reactions may require premature explantation.

**Displacement.** Shifting and rotation of the expander/injection site may occur. Displacement may make the injection site difficult to locate and require surgical intervention.

**Effects on bone.** Chest wall compression has been reported in association with the use of tissue expanders for breast reconstruction.

## Form B: Medical IRB Research Description

Changes in sensation. The expansion process may affect sensation. Sensation may increase or decrease, temporarily or permanently.

Discomfort/distortion. Tissue expansion in an intensive process that causes temporary discomfort and distortion.

### **10. Safety Precautions**

Provisions to guard against the potential risks and discomforts discussed in section 9 are as follows: Every precaution to prevent a direct study injury will be taken by medical personnel and the investigators. Should an adverse or serious adverse event occur, the research participant will be followed by physicians, registered nurses and other research staff members for the duration of the participant's hospitalization and recovery. Routine care will be provided by hospital staff. Emergency medical equipment, medications and supplies will be at the physician's disposal should the participants have an acute untoward reaction.

All patient information used in this study will be de-identified for purposes of the study. Once enrolled in the study, the patient's identifiable information will be replaced with a study number and will be followed using this number in all recording and correspondences throughout the study. Only the PI and the PI's team will have access to identifiable information prior to the patient's enrollment into the study.

### **11. Benefit vs. Risk:**

There is no guarantee that a participant will receive any benefit from taking part in this study. The information from this research may decrease complications associated with breast reconstructive efforts. This may benefit society in the future and is not expected to benefit the individual subject. The risks to subjects are no greater than those from the surgical procedure alone and are reasonable in relation to the importance of the potential knowledge to be gained.

### **12. Available Alternative Treatments:**

If participants do not want to take part in the study, there are other choices such as:

- No reconstruction
- Use the existing single port expander
- Autologous tissue reconstruction

### **13. Research Materials, Records, and Privacy:**

For all participants, records from University of Kentucky Plastic Surgery Clinic will be reviewed to determine study inclusion by [name]. Participants will be given a unique numerical identifier to be used to link Protected Health Information to study data, assigned by the principal investigator. Protected Health Information will be kept in a separate password protected file on the desktop computer of the principal investigator, accessible only to the principal investigator and members of the research team. The computer is in a locked office. Demographic data on age (year of birth), race, gender and past medical history

## Form B: Medical IRB Research Description

will be collected from all participants. This data will be stored in a password protected spreadsheet kept on the desktop computer. Although all data will be entered on to the computer a printed copy of the datasheet is available upon request. Data collected from the study will be linked to the numerical identifier and tabulated in a coded chart so as to keep the participant's personal information private.

### **14. Confidentiality:**

Data will be stored on the office computer of the principal investigator in password protected files. The office is located in the Kentucky Clinic, Division of Plastic Surgery, [name]. Following review of all records and completion of data collection, all files containing Protected Health Information will be deleted so that no link exists between the data and the participant identifiers. No personal identifiers beyond name and medical record number will be stored. Data collected are automatically entered into a spreadsheet table using numeric identifiers only used in analysis, further diminishing any link Protected Health Information. This includes any and all dates, which cannot be back calculated. The protected health information will be destroyed within six months of completion of the study.

We will make every effort to keep confidential all research records that identify the participants to the extent allowed by law.

Participant information will be combined with information from other people taking part in the study. When we write about the study to share it with other researchers, we will write about the combined information we have gathered. Participants will not be personally identified in these written materials. We may publish the results of this study; however, we will keep the participant's name and other identifying information private.

Electronic data with PHI are stored in the University of Kentucky's medical database that has limited medical personnel access, is password protected, and monitored for abnormal activity. Incidental materials containing participant identifiers will be shredded or incinerated.

Officials of the Food and Drug Administration, the University of Kentucky, and the manufacturer of the AlloX2 expander may look at pertinent portions of the records that identify the participant.

### **15. Payment**

No incentives or monetary payment will be given in this study.

### **16. Costs to Subjects**

Either the participant or their insurance company, Medicare or Medicaid will be responsible for the costs of all care and treatment a participant receives during this study that they would normally receive for their condition. These costs that are considered medically reasonable

## Form B: Medical IRB Research Description

and necessary and will be part of the care a patient would receive if they did not take part in this study.

The manufacturer of the AlloX2 expander is not offering any indemnification for their device as there are no increased risks over the other currently available types of expanders.

**17. Data and Safety Monitoring:** Not applicable

**18. Subject Complaints:** Participants are free to ask any question they may have about the study. Participants will be directed to the Principal Investigator if complaints, concerns, or questions arise and provided with contact information. Participants will also be advised to contact the staff of the Office of Research Integrity at [contact] or toll free at [name] with any concerns.

**19. Research Involving Non-English Speaking Subjects or Subjects from a Foreign Culture:** Not applicable.

**20. HIV/AIDS Research:** Not applicable

**21. PI-Sponsored FDA-Regulated Research:** Not applicable.

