## Form B: Medical IRB Research Description

Methods to reduce and treat complications have focused on operative technique and not on the tissue expander itself. The AlloX2 tissue expander has been developed specifically to reduce and treat these complications. The traditional tissue expander has a single port to allow injection of saline through the skin directly into the expander for gradual stretching of the overlying skin. The AlloX2 expander has the same injection port plus a second port which is connected to a perforated drain placed on the lower edge of the expander (see attached diagram). The location of both ports are identified by a magnet placed over the breast skin. This second port gives percutaneous access to the peri-expander space, thus allowing removal of seroma fluid under the mastectomy skin flaps. Seroma aspiration using this access port in the expander is safer than percutaneous aspiration, as it will reduce the potential for accidental puncture of the expander during standard percutaneous drainage. The aspirated fluid can be cultured in the setting of infection allowing identification of bacteria and determination of antibiotic sensitivities. Additionally, instillation of culture specific antibiotic solutions directly into the peri-expander space can be accomplished through the second port. Thus, use of this second port in the expander can be both diagnostic as well as therapeutic.

The AlloX2 expander is FDA approved, but randomized prospective controlled studies have not been done comparing it to the standard single port expander for equivalency. The ability to decrease reconstructive failures related to seromas will benefit patients undergoing post-mastectomy reconstruction and potentially will reduce the costs involved in treating complications.

FDA Indications for Use: 510(k) Number K140383 (letter attached)

“AlloX2 Tissue Expanders are intended for temporary (less than six months) subcutaneous or submuscular implantation to develop surgical flaps and additional tissue coverage required in a wide variety of applications, particularly to aid in reconstructions following mastectomy, to aid in the treatment of underdeveloped breasts and to aid in treatment of soft tissue deformities.

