### 2. Objectives

The goal of this study is to compare the AlloX2 expander with the traditional single port expander for equivalency. Complication rates that will be tracked include seroma, mastectomy skin flap necrosis, infection, wound dehiscence, need for explantation of the expander. Management of seromas will be compared between the two groups. We hypothesize that the AlloX2 expander will be as effective in achieving the final outcome of completion of the second stage of reconstruction with equal or improved complication rates.

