## Form B: Medical IRB Research Description

expander breast reconstruction. Due to the nature of the surgery, the study cannot be blinded. Patients will be followed until completion of expansion and exchange for the permanent implant which typically takes 2 to 3 months. Risks factors that have been previously identified to be associated with increased postoperative complications include smoking, obesity, breast size, diabetes, radiation therapy, and expander fill volume will be identified. The final outcome is completion of expansion and exchange to permanent implant.

Standard operative procedure and postoperative care will be done. Both groups will have the same to external drains placed which is standard operative procedure. Complications will be noted at each postoperative clinic visit and entered into a database. Complication rates will be compared between the two groups and associations with risk factors will be analyzed. There will be no cross-over into the other group in case of reconstructive failure. Treatment failures will be treated in the same fashion in the two groups.

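### Safety monitoring is marked not applicable, and no by-arm review of complications, responsible role or route to the IRB is planned before the end of the study, although absence of added risk is the hypothesis under test

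*Combined protocol and SAP*

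**What the plan says.** Section 17 reads, in full, "17. Data and Safety Monitoring: Not applicable".

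The text that bears on safety elsewhere is as follows.

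- **Outcomes.** Section 2 lists the complications to be tracked: "seroma, mastectomy skin flap necrosis, infection, wound dehiscence, need for explantation of the expander". Its hypothesis is that AlloX2 will achieve "completion of the second stage of reconstruction with equal or improved complication rates".
- **Prior evidence.** Section 1 says that "randomized prospective controlled studies have not been done comparing it to the standard single port expander for equivalency". It also gives infection and/or seroma rates of up to 12-18% when dermal matrix is used, and says that complications can lead to more surgery, hospitalization, expander removal or abandoned reconstruction.
- **Data capture.** Section 3: "Complications will be noted at each postoperative clinic visit and entered into a database". Section 7 has patients seen weekly. Section 3 says that complication rates will be compared between groups, but gives no time for this.
- **Individual events.** Section 10: "Should an adverse or serious adverse event occur, the research participant will be followed by physicians, registered nurses and other research staff members". This concerns care of the affected participant.
- **Statements on risk.** Section 16, explaining why the manufacturer offers no indemnification, says "there are no increased risks over the other currently available types of expanders". Section 11 says "The risks to subjects are no greater than those from the surgical procedure alone".

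**The concern.** There are two linked but separate problems.

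First, the trial randomizes patients between two implanted devices and its complication outcomes are harms, but the plan has no step at which anyone must look at those harms by arm while patients are still being enrolled. The data will exist, because they are entered at every visit. What is missing is a duty to tabulate them, a person responsible, and a route to the IRB. Four infections among patients in one arm could each be treated properly as individual events without anyone having to ask whether they form a pattern.

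Second, Sections 11 and 16 state as settled what Section 2 sets out to test. A protocol that tells the IRB there is no added risk, while saying that no randomized comparison exists, gives its readers a reason to think monitoring is unnecessary.

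At stake is the safety of patients enrolled later, if one device causes more infections or expander losses than the other.

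**Working it through.** The plan gives no monitoring boundary, error rate, power or margin, so there is no figure of its own to reproduce. The check asks whether an interim review could come early enough to matter, and what a simple count could detect.

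**Inputs from the protocol.** 60 patients, 30 per arm, enrolled over 12 months (Section 4). Follow-up to implant exchange, typically 2-3 months (Section 3). Infection and/or seroma at up to 12-18% (Section 1).

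**Assumptions.** Uniform accrual; independent patients; the 12-18% read as a per-patient rate (the protocol does not say whether it is per patient or per breast); a doubled rate as the example of harm.

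**1. Timing.** Accrual is 60 / 12 / 2 = 2.5 per arm per month.

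| Review point | Last of these implanted | Follow-up complete | Implanted per arm by then | Still to be implanted per arm |
|---|---|---|---|---|
| First 10 per arm | 10 / 2.5 = month 4 | months 6-7 | 2.5 × 6 = 15 to 2.5 × 7 = 17.5 | 12.5-15 |
| First 20 per arm | 20 / 2.5 = month 8 | months 10-11 | 25 to 27.5 | 2.5-5 |

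The first look therefore comes with 42-50% of each arm (12.5/30 to 15/30) not yet exposed. The second adds less. Complications that appear before exchange would be visible sooner.

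**2. What a simple count detects.** Take, purely as an illustration, a flag at 4 or more events among the first 10 patients in an arm: P(X ≥ 4) = 1 − Σ C(10,k) p^k (1−p)^(10−k), for k = 0 to 3.

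| True rate | Chance of a flag, one arm, one look |
|---|---|
| 12% | 1 − (0.2785 + 0.3798 + 0.2330 + 0.0847) = 2.4% |
| 18% | 1 − (0.1374 + 0.3017 + 0.2980 + 0.1745) = 8.8% |
| 24% (12% doubled) | 20% |
| 36% (18% doubled) | 51% |
| 40% | 62% |
| 50% | 83% |

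The first two rows are false flags. With both arms checked at one look, the chance of at least one false flag is 1 − (1 − 0.0239)² = 4.7% at 12% and 1 − (1 − 0.0883)² = 16.9% at 18%.

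**3. Size of the harm.** If AlloX2 doubled the rate, the expected excess among its 30 patients would be 30 × 0.12 = 3.6 to 30 × 0.18 = 5.4 events.

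**4. Whether the final comparison would serve instead.** At 30 per arm, a two-sided 5% Fisher exact test has about 13% power to detect 12% against 24%, and about 26% to detect 18% against 36%. A doubling would usually go undetected at the end as well.

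**5. The statements on risk.** Section 1 (no randomized comparison done) and Section 2 (equal or improved rates as hypothesis) cannot both stand beside Sections 11 and 16 (no added risk as fact). This needs no arithmetic.

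**The case against.** The strongest case on the other side is that the study is small, single-center and open label, with short follow-up, and the device is FDA-cleared. Patients are seen weekly, the team knows each patient's arm, and Section 10 provides for care after an adverse event. Section 17 is one field of an IRB form whose instructions are not in the documents; the entry may mean only that no formal plan was required.

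Much of this stands, and it rules out three stronger readings.

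- **That harms would not be looked for until all 60 patients are implanted.** A reader might infer this, but the documents do not say it. The between-group comparison has no stated time, and an open-label team may notice an excess.
- **That the plan forbids monitoring.** A field marked not applicable omits a plan; it does not prohibit review.
- **That the indemnification sentence is the reason for the Section 17 entry.** The documents do not connect the two. Its conflict with Sections 1 and 2 is a separate matter of wording.

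A formal monitoring board is not needed to close the gap, and none is asked for. The illustrative count also has limits. It is a weak detector of a doubling, and its error rates apply to infection and/or seroma only. The documents give no base rate for a wider composite including explantation or serious adverse events.

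What survives is narrower: noticing cases informally is not an obligation on a named person to tabulate them by arm and report them.

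**Conclusion.** The point holds in this form: the protocol plans no aggregate by-arm safety review, no responsible role and no IRB escalation route before the end of the study, and in two places it asserts as fact the absence of added risk that it sets out to test. It should be corrected, and the correction is cheap.

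Under uniform accrual, a review of the first 10 patients per arm with full follow-up would come while 12.5-15 per arm remain to be implanted. Slower accrual than planned would move the looks later in calendar time but leave more patients still to be implanted at each. A count of events can be expected to reveal a large excess and will often miss a doubling (20-51% detected in the illustration). The case rests on the missing duty to look, not on any particular threshold.

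**What to change.** Replace the Section 17 entry with a short harm-only plan:

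- A named role on the existing team tabulates seroma, infection, skin flap necrosis, dehiscence, explantation and serious adverse events by arm at set points, for example after 10 and 20 patients per arm, and sends the table to the IRB. State whether each look waits for full follow-up.
- The investigators and the IRB set in advance what triggers an IRB review. If they use a count, they should state its false-flag rate for both arms and all looks, and the event definition to which it applies.
- The plan says that these looks are for harm only and are never used to conclude equivalence.

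Reword Sections 11 and 16 so that absence of added risk is the hypothesis under test.

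The cost is two tabulations from data already collected, plus wording changes. No committee, extra staff, visits or patients are needed. The downside is an occasional false flag, each costing a short IRB review.
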